**Key words:**

Dyspareunia  
Genitourinary syndrome of menopause (GSM)  
Female Genital Atrophy  
Female Genital Disorder  
Female Sexual Dysfunction (FSD)  
Vaginal dryness  
Vaginal Itching

**Start Date:**

2/10/ 2022

**End Date:**

22/01/ 2024

## List of Abbreviations

ARS-LVT – Regional Health Administration of Lisbon and Tagus Valley  
ciTechCare – Center for Innovative Care and Health Technology  
COSMIN – Consensus-based Standards for the Selection of Health Measurement Instruments  
DIVA – Day-to-day Impact of Vaginal Aging  
EQ-5D – EuroQol Group 5-Dimension Quality of Life Questionnaire  
EQ-VAS – Visual Analog Scale associated with the EQ-5D questionnaire  
FMUM – Faculty of Medicine, University of Minho  
FDD – Digital Data File  
FSFI – Female Sexual Function Index  
HDMA – Hospital Dom Manuel de Aguiar  
HSA – Hospital Santo André  
CHL – Hospital Center of Leiria  
ICVC – Institute for Health Sciences Research  
IPL – Polytechnic Institute of Leiria  
SGUM – Genitourinary Syndrome of Menopause  
UCSP – Personalized Health Care Unit  
UM – University of Minho

This study protocol is part of a PhD project in Medicine to be developed in partnership between the University of Minho, ciTechCare, and the company DRT Molds. The project has been awarded a PhD scholarship by FCT (ref. 2021.07973.BD). The title of the project is "Regenerative Treatment for Vulvo-Vaginal Atrophy". To assess pre- and post-therapy, it was necessary to include clinical assessment instruments, which, in the case of genital atrophy, include self-assessment questionnaires and the perception of the impact that this clinical problem has on a woman's life. As there are no validated questionnaires in European Portuguese, it is intended to proceed with the cultural adaptation of a questionnaire developed in another sociodemographic context. The DIVA (Day-to-Day Impact of Vaginal Aging) questionnaire was selected because it was designed and constructed according to the guidelines of the COensus-based Standards for the selection of health Measurement INstruments (COSMIN), and the construct validity showed adequate values with a comparative fit index of 0.987 and Cronbach's alpha values ranging from 0.82 to 0.93.

We began by informing the authors of the DIVA questionnaire that we would initiate this cultural and linguistic adaptation process, emphasizing that the authors state in the original publication that formal authorization is not required, but they wish to be informed of the results of the translation and cultural adaptation process.

Before the start of this research protocol, a translation process into Portuguese was carried out according to the principles of good practice, which included the following steps: 1) translation by two independent researchers, 2) reconciliation, 3) back translation by two certified translators fluent in English, 4) unification and harmonization of the translated version in Portuguese, 5) evaluation by a group of specialists in gynaecology and sexology, and 6) pre-test in a group of patients with the final cultural adaptation of the DIVA scale translated into European Portuguese.

## **Project Rationale**

Symptoms that cannot be directly quantified but have an impact on quality of life can be assessed through self-perception health questionnaires. These clinical instruments play a key role, not only in identifying the clinical problem but also in assessing the individual impact of the problem on various psychological and physical dimensions, helping to identify the impact of therapeutic strategies on the improvement of these subjective symptoms. For research to be valid, these instruments must be appropriate and accurate to ensure the quality of the results.

Aging has a significant impact on women's genital health, which results in a set of symptoms and signs known as the Genitourinary Syndrome of Menopause (GSM). This clinical issue affects approximately 50% of postmenopausal women. While the urinary component of GSM can be quantified through validated diagnostic tests, the vulvovaginal atrophy component is not quantifiable by diagnostic tests. It has an increasing severity with age, impacting self-esteem, well-being, and sexuality, yet remains a stigma for women and is poorly perceived by doctors. It is in this context that the DIVA questionnaire (Day-to-day Impact of Vaginal Aging) was developed, as it brings together characteristics that make it practical for use in population studies, transforms subjective measures into objective, quantifiable, and analysable data, and assesses the relative strength of each domain or

component of female genital atrophy on quality of life. Other advantages of this questionnaire include being a well-studied and validated index with the ability to evaluate therapeutic interventions. It has also been adapted into other languages besides English – including Spanish, Italian, German, and Turkish – and has been validated in these cultural contexts.

The DIVA questionnaire analyses and quantifies the impact of female genital aging. It consists of 23 items grouped into 4 constructs, which include the dimensions of daily activities, emotional well-being, sexual function, and self-esteem and body image. There are two versions of the questionnaire: the full version with 23 items, which includes 4 items on sexual function that can only be evaluated in sexually active women, and a shorter version with 19 items that can be applied regardless of sexual activity. Each item is rated on a 5-point Likert scale, with the dimension value obtained by calculating the average of the corresponding items. Higher values indicate a greater adverse impact of atrophy symptoms.

---

### **Project Objectives:**

**General Objective:** To determine the reliability, consistency, and validity of the psychometric properties of the Portuguese version of the DIVA questionnaire, adapted for our culture, in peri- and postmenopausal women. This validation will provide the foundation for using this questionnaire both in research and clinical practice with Portuguese women.

**Specific Objective:** To assess the discomfort of genital atrophy symptoms in the study participants and the impact of this problem on the quality of life of peri- and postmenopausal women in the Portuguese context.

### **Materials and Methods:**

#### **Study Type:**

This will be an observational, cross-sectional, and descriptive study, conducted and guided by investigators with the appropriate professional qualifications to carry out the research protocol, in a clinical and human environment suitable for the study. The study will be conducted in accordance with Law No. 21/2014 of April 16 (amended by Law No. 73/2015, July 27) and Decree-Law No. 145/2009 of June 17.

#### **Population and Study Location:**

Participants will include women that had at least one complaint of vaginal atrophy (dryness, itching, burning, irritation, discomfort, or pain when urinating or during intercourse, or bleeding during intercourse, affecting the external genitalia: vulva or vagina).

For the normative convenience sample from the general population, participants will be users of a large urban health centre, the Personalized Health Care Unit (UCSP) of Sete Rios, Lisbon. For the clinical convenience sample, participants will be users of a general gynaecology consultation at a private hospital (Hospital Dom Manuel de Aguiar) and the gynaecology consultation at a public hospital (Hospital Santo André), both located in an urban centre in Leiria, another group of participants came from a private gynaecologic consultation of north of Portugal, at Braga city, aiming to gather 230 valid tests, following COSMIN recommendations, to allow for an assessment of invariance correlation.

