## **Data Collection Instruments:**

The methodological approach is a cross-sectional descriptive study of qualitative and quantitative data, including dependent and independent variables organized into a self-administered form completed by the participants. This form includes 5 questionnaires:

1. **Symptom Questionnaire:** This questionnaire will screen participants to be included in the study who must report at least one symptom associated with genital atrophy. The symptoms include dryness, itching, burning, irritation, discomfort or pain when urinating or during intercourse, or bleeding during intercourse, with each symptom rated on a 5-point Likert scale from 0 (no discomfort) to 4 (extreme discomfort) (Annex 2).
2. **Sociodemographic and Clinical Questionnaire:** This questionnaire will characterize the study participants. The sociodemographic section will include variables related to biological profile, such as gender and birth date, as well as socioeconomic variables like marital status, education, and professional activity. Finally, it will cover clinical variables related to gynaecological function, comorbidities, and treatments (Annex 3).

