#### **4. Inclusion and Exclusion Criteria:**

**Inclusion Criteria:** Women who agree to participate in the study after giving their informed consent (Annex 7) and who report at least one symptom related to genital atrophy, such as dryness, itching, burning, irritation, discomfort, or pain when urinating or during intercourse, or bleeding during intercourse, affecting the external genitalia (vulva or vagina).

**Exclusion Criteria:** Pregnancy, neoplasms under treatment, inability to speak Portuguese, or any mental or physical disability that prevents coherent responses to the questionnaire.

---

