#### **5. Recruitment Model:**

The recruitment for the project will be conducted by the researchers involved, and the selection of participants will be voluntary and carried out on a convenience basis, in a non-random manner.

In all cases, the referred participant must give prior informed consent for referral, by signing the informed consent form and verifying that they meet the inclusion criteria and none of the exclusion criteria.

---

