## **8. Process Implementation:**

- Provision of "Link" at the selected data collection units the materials (questionnaires, informed consents, and envelopes).
- Distribution of data collection materials to data collection units by colleagues interested in collaborating.
- Identification of participants in the clinic, either because they express complaints or through regular medical history taken during consultation.
- Invitation to identified participants to complete the questionnaire in the nearest waiting room, in a more private space designated for the process.
- Sealing of the envelope in person in the consultation room and placing it in a closed box with a slot for insertion.
- Return of completed questionnaires to the Principal Investigator.

---

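### The protocol contradicts itself on which DIVA sexual-function items every woman answers and is scored on; separately, its normative sample is a symptomatic one

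*Protocol*

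**What the plan says.** **Sexual-function items.**

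- Project Rationale: a full form of 23 items, four of which suit only sexually active women, and "a shorter version with 19 items that can be applied regardless of sexual activity".
- Data Collection Instruments, DIVA entry: women without sexual activity have a version with a not-applicable option for the sexual-function domain. The entry does not limit the option to particular items.
- Annex 1 (Portuguese form): a not-applicable box under each of items 10 to 18.
- Annex 4 (English form): the box appears on items 12, 13 and 15, and not on items 10, 11, 16, 17 and 18. Item 14 is absent from the text as read, and nothing here rests on it.
- Annex 4, Recommended scoring: the prose gives a short scale of five items for all women and a long scale of nine, the extra four being 12 to 15. The short-version list below it names six items: 10, 11, 12, 16, 17 and 18.
- Annex 4, Permissions: modifications are allowed but should be identified in publications.
- Data Collection Instruments, FSFI-6 entry: this scale serves the convergent assessment of the DIVA sexual domain.

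**Sample label.** Population and Study Location opens with "Participants will include women that had at least one complaint of vaginal atrophy" and then says "For the normative convenience sample from the general population, participants will be users of a large urban health centre". Data Collection Instruments describes participants "who must report at least one symptom associated with genital atrophy", and the inclusion criteria admit women "who report at least one symptom related to genital atrophy". Recruitment is "carried out on a convenience basis, in a non-random manner", by "Identification of participants in the clinic, either because they express complaints or through regular medical history taken during consultation".

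**The concern.** The general objective is to establish the reliability and validity of the Portuguese DIVA. The short sexual-function scale exists so that every woman can be scored on that domain, whether or not she is sexually active. Two things work against it.

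First, the only item-level scoring key in the protocol names a different short scale from the one its own prose describes. An analyst who follows the list computes a different score, and one that calls for an item the same section reserves for women with recent sexual activity.

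Second, the form under validation offers a way out of exactly the five items that the English form asks of everyone. A woman who uses it throughout has no sexual-function score, short or long. The convergent analysis against the FSFI-6 then has fewer women than the short version was designed to allow, and those lost are selected by sexual inactivity.

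The sample label is a separate and smaller matter. It affects how the Sete Rios group, and any comparison of it with the gynaecology group, is described.

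**Working it through.** **1. Items per version.** The domain lists in Annex 4 give daily activities 5 items (1 to 5), emotional well-being 4 (6 to 9), and self-concept and body image 5 (19 to 23).

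- With the five-item short scale of the scoring prose: 5 + 4 + 5 + 5 = 19. This reproduces the Project Rationale.
- With the nine-item scale: 5 + 4 + 9 + 5 = 23. This reproduces the full version.
- With the short-version list as printed: 5 + 4 + 6 + 5 = 20. This matches nothing else in the protocol.

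Taking the reserved items 12 to 15 from items 10 to 18 leaves 10, 11, 16, 17 and 18. These are the items on which the English form prints no not-applicable box. The Project Rationale, the scoring prose and the English form therefore agree, and the list is the outlier.

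**2. Effect of item 12 on the short score.** Let m be the mean of items 10, 11, 16, 17 and 18, and x the answer to item 12.

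- Six-item mean minus five-item mean = (5m + x)/6 − m = (x − m)/6.
- For a 1-point gap between x and m: 1/6 = 0.17 points on the 0 to 4 scale.
- Example: m = 2 and x = 3 give (10 + 3)/6 = 2.17 instead of 2.00.
- Arithmetic limit: x = 4 and m = 0 give 4/6 = 0.67. This is an extreme answer pattern, not an expected shift.

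**3. Response options side by side.**

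| Items | Scoring prose, Annex 4 | English form, Annex 4 | Portuguese form, Annex 1 |
|---|---|---|---|
| 10, 11, 16, 17, 18 | all women | no not-applicable box | not-applicable box |
| 12, 13, 15 | recent sexual activity only | not-applicable box | not-applicable box |
| 14 | recent sexual activity only | not in the text as read | not-applicable box |

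A woman who marks all nine boxes has answered 23 − 9 = 14 items, and none in the sexual domain. The English form, on the items shown, would still give her five answers and a short score.

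**4. Sample label.** The symptom condition appears in Population and Study Location, in Data Collection Instruments and in the inclusion criteria, with no exception for Sete Rios. No symptom-free woman can enter, so the group is not a sample of the general population. Both groups consist of symptomatic women recruited in clinics.

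**The case against.** The best defence is that the conflict is narrow. The extra 12 looks like a slip in an annex that sets out the source instrument's scoring, and the surrounding prose and the Project Rationale leave little doubt about the intended set. A sexually inactive woman can mark item 12 as not applicable, so it need not enter her score. The wider not-applicable option is disclosed in the DIVA entry, and the permission terms allow modifications. The opening of Population and Study Location states the symptom requirement and both groups are called convenience samples, so eligibility itself is clear.

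Much of this stands. The slip is easy to correct, disclosure is not breached, and the label is a matter of wording. What does not fall away is that the printed key gives a different score if followed, and that the Annex 1 form undoes the purpose of the short scale. A statistical analysis plan could restate the key, but it cannot restore answers the form did not collect.

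Three stronger readings should be resisted.

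- A reader might infer that "aiming to gather 230 valid tests" is tied to no item set, or is too few. The protocol says nothing contradictory about 230. It equals 10 × 23, which fits the full form, although no such ratio is stated. The meaning of a valid test may be left to an analysis plan that is not shown.
- A reader might try to compute how many women lack a score. That needs the share who are sexually inactive and how they use the box, and the protocol gives neither.
- A reader might infer from the label that population norms will be produced. The protocol plans no norm tables.

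**Conclusion.** The main point holds. The protocol is inconsistent on the sexual-function domain in two places: the short-version list in Annex 4, and the not-applicable options in Annex 1 with the matching DIVA entry in Data Collection Instruments. The list shifts the short score by 0.17 points per 1-point gap between item 12 and the mean of the other five. This is pure arithmetic and assumes only that the list is applied as printed. The form permits, but does not force, the loss of the whole domain score for a sexually inactive woman. The consequence for the FSFI-6 comparison depends on how many used the option, which only the data can show.

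The sample label is a separate, minor misdescription: it contradicts the protocol's own eligibility rule but changes no stated analysis.

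**What to change.** 1. Correct the short-version list in Annex 4, Recommended scoring, to items 10, 11, 16, 17 and 18.
2. Reconcile the Project Rationale, the DIVA entry in Data Collection Instruments, Annex 1 and the scoring text on which sexual items are for all women and where not applicable may be marked.
3. Report how many women marked not applicable on items 10, 11 and 16 to 18, and how many then have a short score and a nine-item score. Base these counts on the questionnaire's own answers. Annex 3, question 16, asks about current sexual activity and years without intercourse, whereas the not-applicable box refers to recent activity of any kind, so use question 16 for description only. Give the number of women in the FSFI-6 comparison.
4. Report the added not-applicable option as a modification, as Annex 4, Permissions, asks.
5. Separately, in Population and Study Location, call the Sete Rios group a symptomatic primary-care convenience sample, and describe any comparison of the two groups as primary care versus gynaecology consultation.

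The cost is some wording, one scoring correction and a few counts, with no extra enrolment. The repair is incomplete: the Timeline dates data collection from October 2022 to January 2024, and if the Annex 1 form was used, answers given as not applicable on items 10, 11 and 16 to 18 cannot be recovered.

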## **Data Collection Instruments:**

The methodological approach is a cross-sectional descriptive study of qualitative and quantitative data, including dependent and independent variables organized into a self-administered form completed by the participants. This form includes 5 questionnaires:

1. **Symptom Questionnaire:** This questionnaire will screen participants to be included in the study who must report at least one symptom associated with genital atrophy. The symptoms include dryness, itching, burning, irritation, discomfort or pain when urinating or during intercourse, or bleeding during intercourse, with each symptom rated on a 5-point Likert scale from 0 (no discomfort) to 4 (extreme discomfort) (Annex 2).
2. **Sociodemographic and Clinical Questionnaire:** This questionnaire will characterize the study participants. The sociodemographic section will include variables related to biological profile, such as gender and birth date, as well as socioeconomic variables like marital status, education, and professional activity. Finally, it will cover clinical variables related to gynaecological function, comorbidities, and treatments (Annex 3).
3. **DIVA Questionnaire (Day-to-day Impact of Vaginal Aging):** This questionnaire assesses the impact of vaginal aging on daily life. The original version was developed by Alison J. Huang (Annex 4), Director of the Department of Medicine at the University of California, San Francisco. It included 745 postmenopausal women, from 2008 to 2012, of multiethnic backgrounds with at least one complaint of genital atrophy (dryness, burning, irritation, and itching) or pain during sexual intercourse. The questionnaire is constructed with a multidimensional scale covering 4 domains: (1) daily activities, (2) emotional well-being, (3) sexual function, and (4) self-esteem and body image. The full version consists of 23 items, with a version for women without sexual activity that includes a "not applicable" option for the sexual function domain. The items are scored between 0 and 4, and the overall score is the average of the scores in each domain, with higher scores indicating a greater impact and severity of genital atrophy symptoms. The internal consistency of the original scale in English ranged from 0.47 to 0.72, with Cronbach's alpha between 0.82 and 0.93. Confirmatory factor analysis showed appropriate structural validity with a comparative fit index of 0.987 and a standardized root mean square residual (SRMR) of 0.038. A measurement property assessment of this symptom evaluation questionnaire identified it as one of the best quality and reliable tools for assessing female genital atrophy (Annex 1 and 4).
4. **EQ-5D** is a generic instrument for measuring health-related quality of life, which generates an index representing an individual's health state. Developed by the EuroQoL group since 1987 and made public in 1990, it is based on a classification system that describes health in five dimensions: mobility, self-care, usual activities, pain/discomfort, and anxiety/depression. Each dimension has three associated severity levels: no problems (level 1), some problems (level 2), and extreme problems (level 3) experienced by the individual. Another measure used is the EQ-VAS, a 20 cm vertical visual analog scale (VAS) ranging from 0 to 100, where 0 is the worst and 100 the best imaginable health. This measure of self-perceived health is

evaluated independently for the subject's self-perception. It is available in over 130 languages in various application formats and was validated for European Portuguese in 2013 by Ferreira. It is considered reliable and valid, showing moderate to high correlations with other health status and quality of life measures for various diseases, and the purpose of using this questionnaire is to verify the concurrent validity of DIVA (Annex 5).

5. **FSFI-6 (Female Sexual Function Index)** is an instrument developed by Isidori, based on the longer version of the original questionnaire but designed for easier clinical use, as it is quick to complete but still maintains good internal consistency (Cronbach's alpha of 0.79) and excellent accuracy for differentiating clinical populations, with sensitivity and specificity above 94%. It was validated in the Portuguese population by Pechorro, including 6 items that evaluate 6 domains of sexuality: desire, satisfaction, excitement, lubrication, orgasm, and pain. This scale will be used for convergent assessment of the sexual domain of DIVA (Annex 6).

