## **9. Data Collection Method:**

After voluntary recruitment and confirmation of inclusion criteria and the absence of exclusion criteria, the possibility of inclusion in the study and the volunteer's willingness to participate will be certified. The Informed Consent Form will be provided for the participant to read carefully, while being verbally informed about the details of the study. Once consent is obtained, the participant will complete the form, which will include the participant ID according to a sequential number assigned to each participant. A researcher will be available for any clarification needed during the self-completion of the form.

---

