#### **7. Bleeding or Unpleasant Odor During or After Sexual Intercourse**

- 1 No Discomfort

- 2 Mild Discomfort
- 3 Moderate Discomfort
- 4 Intense Discomfort

---

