**Of these 7 symptoms, the one that bothers you the most or disturbs your life the most is:**

### **Annex 3: Sociodemographic and Clinical Questionnaire**

**Questionnaire:** \_\_\_\_\_

**Age:** \_\_\_\_\_ years **Height:** \_\_\_\_\_ cm **Weight:** \_\_\_\_\_ kg

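### The Symptom Questionnaire in Annex 2 has no item for pain on urinating, which the protocol lists as a qualifying symptom, and its item 7 merges bleeding with odour

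*Protocol*

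**What the plan says.** Three places in the protocol body give the qualifying symptoms.

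- Population and Study Location: "dryness, itching, burning, irritation, discomfort, or pain when urinating or during intercourse, or bleeding during intercourse".
- Data Collection Instruments, item 1, describing the Symptom Questionnaire: "The symptoms include dryness, itching, burning, irritation, discomfort or pain when urinating or during intercourse, or bleeding during intercourse". This paragraph also gives the form its role: "This questionnaire will screen participants to be included in the study who must report at least one symptom associated with genital atrophy".
- Section 4, Inclusion and Exclusion Criteria: women "who report at least one symptom related to genital atrophy, such as dryness, itching, burning, irritation, discomfort, or pain when urinating or during intercourse", followed by bleeding during intercourse.

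All three include urination. None mentions odour.

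Annex 2 prints seven items. The last reads "Bleeding or Unpleasant Odor During or After Sexual Intercourse". The form closes with "Of these 7 symptoms, the one that bothers you the most or disturbs your life the most is", which confirms the count of seven.

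On sequence, section 9 (Data Collection Method) has the form completed "After voluntary recruitment and confirmation of inclusion criteria and the absence of exclusion criteria" and consent. Section 8 has women identified in the clinic by complaint or history, and the completed questionnaires sealed in an envelope.

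**The concern.** The protocol describes its screening instrument as covering a symptom that the instrument does not ask about, and the instrument asks about one that the protocol does not list.

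Two things are at stake. The first is the status of some forms. The instructions to Annex 2 tell a woman to mark no discomfort for any complaint she does not have. A woman with only pain on urinating could correctly mark all seven items that way. She meets section 4 but fails the screen stated under Data Collection Instruments, and the protocol does not say whether her form counts towards the 230 valid tests.

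The second is the specific objective, which is to assess the discomfort of genital atrophy symptoms. On this form, pain on urinating has no score and cannot be named as the most bothersome symptom, and bleeding has no score separate from odour.

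**Working it through.** No figure in the protocol bears on this point, so the check compares the eligibility list with Annex 2 entry by entry. As punctuated in the population section and section 4, the list has eight entries.

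| Listed symptom | Annex 2 item |
|---|---|
| Dryness | 1 |
| Irritation | 2 |
| Itching | 3 |
| Burning | 4 (also after intercourse) |
| Discomfort | 5 (also after intercourse) |
| Pain during intercourse | 6 |
| Pain when urinating | none |
| Bleeding during intercourse | 7, joined with odour |
| (odour: not listed) | 7, joined with bleeding |

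Seven of the eight listed symptoms have an item and one does not (8 − 7 = 1). One of the seven items combines a listed symptom with an unlisted one.

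**Is an item lost in the printed text?** No. Seven items are printed and the closing line refers to seven.

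**Does another questionnaire fill the gap?** No. The only urinary question in Annex 3 (question 17) concerns leakage on coughing. DIVA item 3 asks about interference with toilet use, which is not a report of pain on urinating. The only pain item in Annex 2 (item 6) is tied to intercourse.

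**What can item 7 show?** Let x be the number of women positive on item 7 and b the number with troublesome bleeding. A woman who marks no discomfort reports trouble from neither, so b cannot exceed x. Every positive answer may be odour alone, so item 7 by itself gives only 0 ≤ b ≤ x.

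**Which route decides inclusion?** Data Collection Instruments gives Annex 2 the screening role. Sections 8 and 9 have women identified and the criteria confirmed before the form is filled in. The two routes use different symptom lists, and no check of one against the other is described.

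**The case against.** The other side has several good arguments, and they limit the point.

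- **Odour.** A reader might infer that women with odour only are admitted against the criteria. The documents do not support this. Section 4 introduces its list with words that leave it open, and Data Collection Instruments also uses inclusive wording. Only the parenthesis in the population section reads as closed. Odour is unlisted, not excluded.
- **Selection.** A reader might infer that Annex 2 turns eligible women away. On the sequence in sections 8 and 9, a woman with only urinary pain may already be included when she completes it, and no passage says that an all-negative form is rejected. What stands is that the protocol gives Annex 2 a screening role which that sequence does not clearly let it play.
- **Coverage.** Both eligibility passages confine symptoms to the external genitalia, so pain on urinating might be entered under burning (item 4) or discomfort (item 5), and a researcher is available to help. Such women would not be lost, but their complaint would be recorded as something else.
- **Wording of the form.** Annex 2 is printed in English, and items 4 and 5 seem to lack words before the reference to intercourse. The form that participants saw might differ. The printed items are nevertheless what the protocol specifies, and none names urination.
- **Importance.** The general objective is the psychometrics of DIVA, with EQ-5D and FSFI-6 as the named comparators. The Project Rationale separates the urinary component from vulvovaginal atrophy, so leaving urination off the form could be deliberate. In that case the three lists are wrong instead, and the conflict still has to be resolved.

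**Conclusion.** The point holds in a limited form. Annex 2 does not match the protocol's own description of it: one of eight listed symptoms has no item, and one of seven items cannot be interpreted when positive. The other listed symptoms are covered.

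The effect on the specific objective is definite: no measure of pain on urinating, and only an upper bound for bleeding that causes discomfort. It would be too strong to say that bleeding cannot be assessed at all, because a negative item 7 is informative. The effect on who enters the study is possible but not established.

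A reader might also want a count out of the 230 valid tests. The documents give no frequency for women with urinary pain only or odour only, so any percentage would be a guess.

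The conclusion assumes that the printed Annex 2 reflects the form in use. It merits a correction, since it affects reported data, but it does not threaten the general objective.

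**What to change.** **Form.** Add an item to Annex 2 on discomfort or pain on urinating, split item 7 into one item for bleeding and one for odour, and update the count in the closing question.

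**Text.** Reconcile the population section, Data Collection Instruments and section 4 with Annex 2. The sponsor should state whether odour alone qualifies, and whether Annex 2 or the clinic history determines inclusion.

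**Forms already collected.** Participant contact was scheduled from October 2022 to January 2024, so this part matters most. Report item 7 as bleeding or odour and never as bleeding alone. Flag women who are positive on item 7 only, and women with all seven items at no discomfort. State that pain on urinating was not measured.

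**Cost.** Two more lines on the form and a short amendment. Earlier forms will lack the new items, and the change cannot repair them.
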